For these reasons, we employed a user-centered design process to design and formatively evaluate the EMBED (Emergency Department-Initiated Buprenorphine for Opioid Use Disorder) CDS intervention. The user-centered design and formative evaluation of the EMBED intervention is reported elsewhere. Given the current opioid epidemic in the US, there is great urgency for prospective trials to identify the best approaches to BUP implementation and integration into routine practice. The goal of this multicenter, pragmatic, parallel cluster randomized trial is to compare the effectiveness of user-centered CDS for ED-initiated BUP and referral for ongoing MOUD treatment to usual care on the rates of ED initiation of BUP and referral in ED patients with OUD. We hypothesize that rates of ED-initiation of BUP and referral will be higher in the user-centered CDS arm of the trial.

4. **Research Plan:** Summarize the study design and research procedures using non-technical language that can be readily understood by someone outside the discipline. **Be sure to distinguish between standard of care vs. research procedures when applicable, and include any flowcharts of visits specifying their individual times and lengths.** Describe the setting in which the research will take place.

Design

The study design is an 18-month pragmatic, parallel, cluster randomized, superiority trial using constrained randomization of clusters to arms (schematic diagram, Figure 1).[27–29] The unit of randomization (i.e. cluster) is the ED. EDs will be randomly allocated with an allocation ratio of 1:1. Adequate lead time will be allotted to install the intervention in the EHR at all intervention sites-- including a three month implementation and washout phase. The intervention will then begin at the same time across all sites with the CDS intervention fully implemented in the intervention sites' EHRs at the start of the trial. Clinicians at control sites will retain all control of their practice and practice as usual without the CDS intervention installed in their EHR.

[figure not shown]

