Pragmatic trials study an intervention under the usual conditions in which it will be applied; as opposed to an explanatory trial which would test an intervention under ideal conditions. [27,30] In cluster randomized trials, treatment intervention is allocated to clusters (i.e. groups of individuals) rather than individuals. This is done to manipulate the physical or social environment of the intervention when an individual intervention would likely result in contamination between intervention and control participants at the group level.[28] The parallel cluster randomized design was chosen over a stepped wedge design due to the high likelihood of confounding by temporal trends from ongoing efforts to mitigate the opioid epidemic.[31][32] A major challenge of the cluster randomized design is from potential confounding due to a limited number of heterogeneous groups.[28] Constrained randomization offers a solution to this source of confounding by balancing key cluster-level prognostic factors across the study to avoid distorting estimates of treatment effect due to the confounding factors.[29] This allocation technique more evenly distributes potential confounders between intervention arms by specifying the confounding factors, characterizing each cluster in terms of these factors, identifying a subset of randomization combinations of clusters that adequately balance confounding factors between intervention arms and randomly selecting one of these combinations as the allocation scheme.[29] Potential confounders that will be used for this trial are: EHR vendor, ED annual volume, ED type (e.g., academic, community, urban, rural, etc), ratio of ED clinicians who have a waiver to prescribe BUP, current rate of ED BUP prescribing, resources in ED to facilitate management of patients with OUD, and willingness of staff to adopt the practice of ED-initiation of BUP.

Intervention

The intervention for this study includes the user-centered CDS as well as education of ED clinicians practicing at all study sites.

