How severe is the patient's withdrawal?	None-to-Mild < 8 DO NOT give if intoxicated	None-to-Mild < 8 DO NOT give if intoxicated	Mild-to-Moderate 8 - 13	Moderate-to-Severe > 13	Diagnose OUD using DSM tool Assess withdrawal using COWS tool Motivate Readiness using interview tool
Is the patient ready to start treatment?	NO Select #1	YES Select #2	YES Select #3	YES Select #4	

The educational plan will be site-specific and tailored to the usual care at that institution. It will be administered within three months of the study start date. The details of the plan will be developed in partnership with local champions who self-identify an interest in helping to implement an ED-initiated BUP protocol at their site. Specifically, the education plan will be required to include:

1. A didactic on opioid use disorder, its diagnosis, assessment of withdrawal severity, and local resources for referral for ongoing MOUD treatment
2. Circulation and posting in each study site ED of the flow diagram of the study's clinical protocol for ED-initiated BUP (**Figure 2**). Since this protocol is considered best practice, clinicians at control sites will retain all control of their practice and be encouraged to follow this protocol even though the CDS will not be available to them.
3. Intervention sites will include strategies to increase use of the intervention by training clinicians on how to launch and use the CDS. Use of the intervention will be tracked with site-specific audit and feedback that is consistent with typical quality improvement initiatives at that site.

Given the ongoing and escalating opioid epidemic and wide scope of this trial, we anticipate that there may be concomitant interventions to stem OUD at study sites during the trial. We plan to permit these interventions as long as they are: (1) implemented before randomization so that they can be tracked and accounted for in the constrained randomization process, and (2) they are not a health IT intervention targeted at clinicians to initiate BUP in the ED.

Outcomes

The primary study hypothesis is that there will be higher rates of provision of ED-initiated BUP with referral for ongoing MOUD with user-centered CDS compared with usual care. Therefore, the primary outcome will be BUP initiation in the ED, defined as whether or not an eligible patient is administered

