BUP in the ED and/or prescribed BUP upon discharge from the ED. Although this is not a patient-centered outcome, it is a pragmatic and meaningful surrogate that will serve as a lead indicator of the CDS intervention's effect on engaging more OUD patients in treatment.

We will also evaluate the effect of user-centered CDS on the following secondary implementation outcomes as compared to usual care, including several following the RE-AIM framework:[\[41,42\]](#)

1. Referral to follow-up for ongoing MOUD treatment (patient-level; Y/N) treatment
2. Prescription for naloxone at ED discharge (patient-level; Y/N)
3. Receipt of discharge instructions on opioid use, overdose education, naloxone education, and buprenorphine education (patient-level; Y/N)
4. Clinician adoption rates (clinician level):
 - a. Provision of any ED-initiated BUP during the trial (Y/N)
 - b. Provision of any referral for ongoing MOUD treatment during the trial (Y/N)
5. Receipt of Drug Addiction Treatment Act of 2000 training during trial (clinician level; Y/N)

Additional secondary implementation outcomes to be obtained from the web application include: clinician fidelity with the intervention assessed via a critical action checklist[\[43\]](#) and error rate of the intervention (using surrogates based on tool usage, e.g., application launched but not used, launching a page in the web application and spending less than two seconds on that page). The intervention will continue to be made available for use after the trial concludes; three months after trial completion, medical record review of eligible patients will be conducted at a subset of intervention sites to determine the maintenance rate of the intervention.

Data Collection

Outcome data will be collected via SQL query of the local EHR at regular intervals from data routinely collected in each hospital's EHR. This will facilitate large-scale data collection that would not otherwise be practical in an explanatory trial.

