Analysis of Secondary Outcomes: Secondary outcomes such as referral for MOUD appointment, attendance at an MOUD appointment (if available in the EHR), prescription for naloxone at ED discharge and receipt of discharge instructions, will be evaluated using random effects logistic regression as described above. Assessments of the clinician including provision of any ED-initiated BUP during the trial, provision of any referral for ongoing MOUD treatment during the trial and receipt of Drug Addiction Treatment Act of 2000 training during the trial will be compared between intervention and usual care using a GLMM. These models will be stratified by the number of eligible patients the clinician encountered during the trial and will include a fixed effect for intervention, cluster-level covariates included in the constrained randomization, and a random effect for ED. Discrete numeric outcomes such as clinical fidelity will be compared using the GLMM with an log link and a negative binomial distribution.

Plan for Missing Data: Several strategies will be imposed to accommodate the likelihood that missing data will occur during this study. Prevention is the most obvious and effective manner to control bias and loss of power from missing data. [48] As noted in the Data Collection section above, prior to the trial we will pilot data collection procedures. Variables with large proportions of missing will be excluded from collection. We will follow the intent to treat principle, requiring follow-up of all EDs randomized regardless of the treatment received. [49] Regular data retrieval from EHR combined with monitoring

and missing data reports will trigger protocols for tracking and obtaining missing data. Despite these prevention efforts it is reasonable to assume missing data will occur. Our primary analysis is valid under the assumption that missing data is missing at random (MAR).[\[50\]](#) We will evaluate the plausibility of this assumption by determining the extent of missing data and use logistic regression to identify factors associated with missing data. As appropriate, we will conduct sensitivity analysis using pattern-mixture and selection models under missing not at random (MNAR) assumptions to examine the robustness of conclusions of the primary analysis to missing data.[\[48,50\]](#)

SECTION II: RESEARCH INVOLVING DRUGS, BIOLOGICS, RADIOTRACERS, PLACEBOS AND DEVICES

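### Does the plan leave the window and clinician set for the DATA 2000 training outcome, and the groups for CDS fidelity, too open to analyse?

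*Combined protocol and SAP*

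**What the plan says.** The training outcome is a clinician-level yes/no item in the Outcomes list (Section I, item 4). Item 13 states that "receipt of Drug Addiction Treatment Act of 2000 training during the trial will be compared between intervention and usual care using a GLMM", in models "stratified by the number of eligible patients the clinician encountered during the trial" with a fixed effect for intervention, the cluster-level covariates from the constrained randomization and a random effect for ED. Those covariates include the "ratio of ED clinicians who have a waiver to prescribe BUP".

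On timing, the Design text allows lead time for installation, "including a three month implementation and washout phase". It continues: "The intervention will then begin at the same time across all sites with the CDS intervention fully implemented in the intervention" sites' EHRs when the trial starts. Of the educational plan, the Intervention text says "It will be administered within three months of the study start date". All sites receive the didactic and the posted flow diagram. Intervention sites add "strategies to increase use of the intervention by training clinicians on how to launch and use the CDS".

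On who is analysed, item 9 makes every clinician working in a study ED eligible. General Considerations in item 13 sets an intention-to-treat analysis of all individuals.

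Fidelity is listed under Outcomes as fidelity with the intervention, taken from the web application. Item 13 gives it a negative binomial model and says it is compared, without naming groups.

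**The concern.** Three things look unsettled.

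- **Window.** Only intervention EDs install the CDS, so allocation must be known before the three-month phase. If counting starts at go-live, a clinician at an intervention ED who is prompted to train during that phase is coded No. The waiver ratio is a randomization factor and so is fixed earlier; adjusting for it would not recover those clinicians. If early training differed by arm, the estimated effect would shift on every scale.
- **Clinician set.** Stratifying on a patient count accrued during the trial raises the question of whether a clinician with a count of zero is kept. Limiting the set to clinicians with at least one eligible patient would define it after randomization.
- **Fidelity.** A comparison with no named groups could be read as CDS against usual care, for a measure that exists only where the tool is used. The tool can also be reached over the Internet, so a launch from a control ED is conceivable.

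**Working it through.** The plan states no training rate, training dates, effect size or total number of clinicians, so there is no figure of its own to reproduce. The check sets the texts side by side and then asks how much each open point could matter on assumed rates.

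**1. Window, from the text.** The outcome counts training during the trial. Design places the start of the trial at go-live, simultaneous across sites, after a phase it calls implementation and washout. A washout is ordinarily left out of outcome counting. The natural start is therefore go-live. Two details stay open: which side of study start the education falls on, and whether the 18 months include the three-month phase.

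**2. Window, in numbers.** From the plan: a 3-month phase and an 18-month trial. Assumed: 10% (control) and 20% (CDS) trained from randomization onward, with control training spread evenly. Counted rate = total rate × (1 − share *s* falling before go-live).

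With the phase ahead of the 18 months, control *s* = 3/21 and the counted control rate is 0.10 × (1 − 3/21) = 0.0857.

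| CDS-arm *s* | CDS rate counted | Difference (points) | Risk ratio | Odds ratio |
|---|---|---|---|---|
| 3/21 (even) | 0.1714 | 8.6 | 2.00 | 2.21 |
| 0.25 | 0.150 | 6.4 | 1.75 | 1.88 |
| 0.50 | 0.100 | 1.4 | 1.17 | 1.19 |

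With the phase inside the 18 months, control is 0.10 × 15/18 = 0.0833, and the risk ratio is 0.150/0.0833 = 1.80 or 0.100/0.0833 = 1.20.

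With the same share in both arms, the rates are 0.075 vs 0.150 (*s* = 0.25) or 0.05 vs 0.10 (*s* = 0.50). The risk ratio is 2.00 either way.

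A harsher case takes 20% vs 30% and puts none of the control training in the phase. For CDS-arm shares of 0, 0.25 and 0.50 the difference is 0.30 × (1 − *s*) − 0.20 = +10, +2.5 and −5 points.

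So the result moves only when *s* differs by arm, and every unequal *s* above is an assumption. The only arm-specific education in the plan concerns launching and using the CDS. The didactic required at all sites does not list waiver training either.

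**3. Clinicians already trained.** If a share *w* trained earlier and is coded No, each rate becomes *p*(1 − *w*). At *w* = 0.1: 0.09 vs 0.18, difference 9 points, risk ratio 2.0, odds ratio 2.22. At *w* = 0.4: 0.06 vs 0.12, difference 6 points, risk ratio 2.0, odds ratio 2.14. The absolute difference shrinks, the risk ratio is unchanged, and the odds ratio barely moves from 2.25.

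**4. Clinicians with no eligible patient.** Section III, item 1 gives a Yale target of 800 charts and 200 clinicians, a mean of 4. If those charts are the eligible patients (an assumption), the share with none is exp(−4) = 1.8% under a Poisson count, about 4 of 200. Under a negative binomial count it is (k/(k + 4))^k: 11.1% at k = 2, 20.0% at k = 1 and 33.3% at k = 0.5, the last about 67 of 200. The values of k are assumed.

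For the effect of the set, take 20% vs 30% trained among clinicians with a patient and 5% in both arms among those without. Zero-patient shares of 0%, 20% and 40% give pooled differences of 10, 8 and 6 points (odds ratios 1.71, 1.63, 1.54). The choice of set can matter, but the text makes it: all clinicians are eligible, there is no patient minimum, and all are analysed. Stratifying by a count does not exclude zero, which can be its own stratum.

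**5. Fidelity.** No arithmetic applies. The source is the web application, control EHRs do not have it installed, and the plan says the CDS will not be available to control clinicians. That leaves intervention EDs.

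**The case for a change.** The strongest case for a change is that the natural reading of the window is the one that creates the risk: starting at go-live discards training that follows allocation. A set built from eligible-patient encounters could also lose zero-patient clinicians without anyone deciding to drop them. A few sentences written before outcome data are seen would remove that discretion cheaply.

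Part of this stands. No sentence ties the go-live date to the training outcome, the strata have no categories, the source of training dates is not named (Data Collection mentions an EHR query for outcomes), and the fidelity sentence names no groups. The fidelity gap is the best supported of these.

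The rest does not carry. Counting from go-live is a legitimate definition of the outcome, applied alike to both arms. Where the assumed front-loading does harm, it works against the CDS arm rather than producing a spurious benefit. Dropping zero-patient clinicians would depart from the intention-to-treat statement and the eligibility rule, so it is not something the plan leads an analyst to do. Extra supportive analyses would be a matter of preference. One restricted to clinicians untrained at randomization may need a data element not now collected, and step 3 shows no relative bias for it to correct.

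**Conclusion.** The concern identifies missing detail but no error. Read with the Design, eligibility and intention-to-treat text, the plan supports counting training from CDS go-live, coding clinicians trained earlier as No, keeping clinicians with zero eligible patients, and summarising fidelity within intervention EDs. An analyst would fill these gaps that way.

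The all-clinician comparison by randomized ED is valid as written. The drop in the risk ratio from 2.0 to 1.75 or 1.17 reflects an assumed imbalance in early training; with equal timing in the two arms it stays at 2.0. The 2% to 33% of clinicians without an eligible patient rests on assumed count distributions and on treating the Yale charts as eligible patients. Only secondary outcomes are affected. The conclusion would need another look if records showed DATA 2000 training concentrated before go-live in one arm; nothing in the documents suggests this.
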